#### 11.2.5.3. PREGNANCY NOTIFICATION PROCEDURE

Pregnancies and suspected pregnancies occurring during the study period from the signature of the informed consent form until up to 4 months after withdrawal of investigational medicinal products for female patients and 6 months after withdrawal of investigational medicinal products for female partners of male patients, are immediately reportable events. Every pregnancy or suspicion of pregnancy should be notified to the Sponsor without any further delay.

Pregnancy notification will be done using the "pregnancy notification form" (appendix 11). This form should be completed using the filling instruction guide (appendix 11) and sent by email to the pharmacovigilance unit (see above).

The Investigator should inform the Sponsor of the pregnancy follow-up by using the same "Pregnancy Notification Form" (appendix 11) as for the initial notification. If the outcome of the pregnancy falls within the scope of the definition of serious adverse event (spontaneous

abortion requiring hospitalization, fetal death, congenital abnormality...) the investigator should follow the Serious Adverse Event notification.

If it is a paternal exposure, the investigator must obtain the agreement of the pregnant women to collect the information on pregnancy.

#### 11.2.5.4. SUMMARY CHART OF NOTIFICATION BY TYPE OF EVENT

Type of Event	Notification requirements.	Notification period to the sponsor
Adverse Event	Case Report Form	No Immediately reportable events
Serious Adverse Event	SAE Notification Form ( initial+ Follow up, if necessary) + Case Report Form	Immediately reportable events without any delay to the sponsor
New Event	Written report	Immediately reportable events without any delay to the sponsor
Urgent Safety Measure (USM)	Written report	Immediately reportable events without any delay to the sponsor
Pregnancy	Pregnancy notification form	From confirmation of pregnancy

#### 11.2.6. OBLIGATION OF THE SPONSOR

The ICM, as the sponsor of the trial, receives all SAE Notification Forms and evaluates the imputability and the expectedness of the SAEs. In case of a “New event” or any urgent safety measures, the sponsor shall inform immediately ANSM and the concerned CPP of the new events and the measures taken.

The declaration of eventual SUSARs and “New event” or any urgent safety measures (USM) to the competent authorities is delegated to UNICANCER, [name] ([contact]). UNICANCER submits the SUSARs within the required regulatory timelines to the European Medicine Agency (EMA) via EudraVigilance and the competent national authorities (ANSM).

The risk-benefit balance of the study is evaluated continuously by the Clinical Research Vigilance Unit of ICM and this risk-benefit balance will be discussed in the periodic safety reports. These reports will contain all required regulatory aspects and will be submitted to the competent authority (ANSM) and CPP within the regulatory timeframe.

**SUMMARY CHART OF NOTIFICATION BY TYPE OF EVENT**  
**ART. R1123-53**

Type of Event	Initial notification period to the Competent Authority (ANSM, CPP)	Follow up notification period to the Competent Authority (ANSM, CPP)
SUSARs (Death, or life threatening)	Immediately reportable events With any delay after the sponsor has taken notice of this event	Within maximum 7 days after the sponsor has taken notice of this event
Other SUSARs	Within 15 days after the sponsor has taken notice of this event	Within maximum 8 days after the sponsor has taken notice of this event
New Safety Event	Immediately reportable events With any delay after the sponsor has taken notice of this event	Within maximum 8 days after the sponsor has taken notice
Urgent Safety Measures (USM)	Immediate implementation of MUS Immediate information (without any delay)	Request for substantial modification Within maximum 15 days after the sponsor has taken notice

#### 11.2.7. INDEPENDENT SAFETY COMMITTEE (ISC)

An Independent Safety Committee (appendix 12) is organized as an Independent Data Monitoring Committee, comprising independent experts in clinical research and/or the study indication.

The ISC will be constituted of 3 persons: two oncologists and a methodologist not participating in the trial.

The first scheduled time point will be at the end of phase I. According to the number of DLTs and after the advice of the IDMC, the sponsor will decide to continue on to phase II or stop the trial. The sponsor could ask to organise an additional independent safety committee in the event of SUSARs during Phase I.

During a trial the ISC could be requested to review:

- Real-time and cumulative safety data for evidence of study-related adverse events;
- Adherence to the protocol;
- Factors that might affect the study outcome or compromise the trial data (such as protocol violations, losses to follow-up, etc.);

- Data relevant to proceeding to the next stage of the study, if applicable.

The safety data will be provided to the ISC members by the Biostatistics Unit, and / or the Clinical Research Pharmacovigilance Unit and / or the Study Coordinator.

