	
in 8% of cycles. Oxaliplatin and irinotecan doses were reduced in 11% and 12% and interrupted in 11% and 5% of administered cycles, respectively. Actually, regorafenib had acceptable tolerability in combination with chemotherapy. The most frequent grade 3-4 AEs were: neutropenia (45%), Hand-Foot Skin Reaction (15%), diarrhea (10%), and hypophosphatemia (12%). Regarding pharmacokinetics, area under the curve (AUC) of irinotecan was significantly higher in cycle 2 (following regorafenib dosing) than in cycle 1 (before regorafenib dosing); the ratio of AUC values (cycle 2:cycle 1) was 1.28 (90% confidence interval [CI] 1.06 –1.54). Cmax of irinotecan was only slightly increased, and t1/2 was unchanged. For SN-38, AUC was significantly higher in cycle 2 than in cycle 1 (ratio 1.44, 90% CI 1.12–1.85), while Cmax was unchanged. In line with the known elimination pathways of platinum and 5-fluorouracil, no pharmacokinetic interaction with regorafenib was seen (10). The study from O'Neil et al. (11) was designed to show whether the addition of regorafenib to FOLFIRI improves PFS (over a placebo-FOLFIRI arm) when given as second-line therapy for patients treated initially with oxaliplatin and fluoropyrimidine-based therapy. The regorafenib/FOLFIRI schedule that was used was the one proposed by Schultheis et al. (10) (i.e. standard FOLFIRI with irinotecan 180 mg/m^2 plus regorafenib 160 mg daily from day 4 to 10). The study met its primary endpoint of demonstrating that the addition of regorafenib to FOLFIRI prolongs PFS compared to FOLFIRI alone with a HR of 0.72. When looking at tumor response, authors found that regorafenib (combined to chemo) provided more partial responses than placebo plus chemo (35% vs. 19%, p= 0.045). The combination was very tolerable, with little increase in toxicity compared to the control chemotherapy regimen. Of note, regarding the top-3 reported severe (gr. 3-4) AEs, neutropenia, diarrhea, and hypophosphatemia were reported in 41%, 15%, and 14% of the patients, respectively (as compared to 30%, 5%, and 0% in the placebo group) (11).
 
Actually, there is room to combine regorafenib with a chemo triplet such as FOLFIRINOX (5-fluorouracil, irinotecan, oxaliplatin) on the following conditions: controlling patients on UGT1A polymorphisms (at least UGT1A1), stepwise dose-escalation of irinotecan and regorafenib, mandatory granulocyte growth-factor injections.

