## Phase I

DLT monitoring must be performed during the first three cycles of treatment. Patients will be treated until disease progression.

In case of patient withdrawal before completing the entire third cycle for reasons other than DLT, a new patient will be included at this dose level.

The phase I part of this study will be designed as a standard 3+3 design for dose escalation/de-escalation and 3 to 6 patients will be enrolled in each cohort sequentially, depending on occurrence of dose limiting toxicities (Figure 1).

A standard 3 + 3 design will be followed in the dose escalation part of study.

Three dose levels for Irinotecan/Regorafenib (IRI 150/REGO 120, IRI 180/REGO 120, IRI 180/REGO 160) are planned as well as a -1 level (IRI 150/REGO 80) to be opened in case of maximum tolerated dose (MTD) was reached at level 1 (Table 1).

Table 1 :

Steps	Dose Levels	Number of patients
DL-1	IRI 150/REGO 80	0-6
DL1	IRI 150/REGO 120	3-6
DL2	IRI 180/REGO 120	3-6
DL3	IRI 180/REGO 160	3-6

At each dose level, three patients will be included. Three additional patients will be enrolled at the same dose level if one dose limiting toxicity (DLT) is observed in the first three patients of this dose level (Figure 1).

Figure 1 :

[figure not shown]

Table 2 : Dose escalation rules

Outcome (# DLT / # Patients)	Action
0 DLT out of the first 3 patients	Include 3 patients at the next dose level
1 DLT out of 3 patients	Include 3 additional patients at the same dose level.
$\geq 2$ DLT out of 3 patients	Stop dose escalation. Include 3 additional patients at the previous dose level (unless 6 subjects were already treated).
$\geq 2$ DLT out of 6 patients	Stop dose escalation. Include 3 additional patients at the previous dose level (unless 6 patients were already treated).

The MTD is defined as the dose at which at least two out of three to six patients experienced a DLT during the first three cycles of treatment.

Dose escalation will be stopped if MTD is reached or the last dose level (IRI 180/REGO 160) is reached (MTD not reached).

The recommended phase II dose (RP2D) is defined as the dose closest to the MTD at which a DLT is observed in 0/3 or 1/6 patients.

Should any patient discontinue the study prior to completing the entire (3 cycles) for reasons other than a DLT then a replacement patient will be added at that dose level.

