### **DLT recording and assessment**

- Study sites will document any DLT immediately and report a DLT event to the Sponsor within 24 hours of site's awareness.
- Once recruitment of 3 or 6 patients per dose level has been completed, recruitment will be halted by default until the 3-cycle dose-finding treatment has been completed for each patient and sites have reported all relevant safety findings.
- The decision to stop, modify or continue escalation will be made by the project team (coordinator, statistician, project manager, safety vigilance head and vigilance manager) if there are no SUSARs. In the event of SUSARs, we will refer the matter to the independent scientific committee.
- The Sponsor will communicate further dosage information (dose escalation or de-escalation) and additional safety measures to all participating sites/investigators.

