Including skin assessment for toxicities

Pre-menopausal women of childbearing potential only

12-lead ECG will be performed before and after the administration of Oxaliplatin during the three first cycles (Phase I and II) beyond cycle 3, ECG will be performed before administration of oxaliplatin

Includes: albumin, creatinine, creatinine clearance calculated according MDRD, lipase, glucose, TSH (every 6 weeks of CXD1), , total protein and uric acid

Liver function tests will be performed weekly during the three first cycles of treatment

Not required at day 1 of cycle 1 if those were completed within 7 days

Dipstick assessment with pH, protein, glucose, bilirubin, ketones, blood cells and leucocytes

CT scan of the abdomen, pelvis and chest or if the patient is allergic to iodine contrast agents, hepatic MRI and CT scan of the pelvis and chest without injection; RECIST criteria version 1.1

CT-Scans will be performed every 8 weeks

If the last radiological tumor assessment > 1 month

CT-Scan of safety follow-up will be performed if only it weren't done at the EOT visit

Period for DLT assessment is the three first cycles (only Phase I)

Height only at screening

Blood pressure will be monitored every other week during the first 3 cycles of treatment

Continuously from screening until FU visit, 30 days after last administration of study drug

A treatment diary will be handed over to patient on cycle 1 day 1

Three EDTA tubes will be collected at baseline, every 8 weeks during treatment and at the end of treatment

Paraffin-embedded human solid tissue blocks will be sent off at room temperature at the end of the enrollments

Only for unstabilized adverse events since the end of treatment

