#### **11.2.2. URGENT SAFETY MEASURE (USM) (ARTICLES L.1123-10 ET R. 1123-62 CSP)**

When a suspicion of an Unexpected Serious Adverse Reaction (SUSAR) or a New Event is likely to affect the safety of the subjects, or the IMP is likely to affect the safety of the participant who lend themselves to it with immediate endangerment, the sponsor and investigator put in place Urgent Safety Measure (USM) to protect the subjects against this immediate hazard, the sponsor and the investigator concerned take the necessary appropriate Urgent Safety Measures (USM).

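### In the supplied text, phase II (63 new patients) has no dated committee review after the end of phase I and no toxicity count that pauses inclusion; appendix 12 should be checked first.

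*Combined protocol and SAP*

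**What the plan says.** **Phase I.** Section 3.1 (Table 2) stops escalation at two or more DLTs in three or six patients. After each cohort of 3 or 6, "recruitment will be halted by default until the 3-cycle dose-finding treatment has been completed for each patient". Section 11.2.7 adds a committee opinion before the sponsor decides whether to open phase II.

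**Phase II.** Section 11.2.7 begins "An Independent Safety Committee (appendix 12) is organized as an Independent Data Monitoring Committee" and gives one date: "The first scheduled time point will be at the end of phase I". The optional extra meeting for SUSARs is tied to phase I. Beyond that, "During a trial the ISC could be requested to review" cumulative safety data, adherence and related matters; no date, patient count or trigger follows. Footnote 14 of the visit schedule (section 5.1) limits DLT assessment to the first three cycles of phase I. Sections 10.1 and 10.3 describe a one-stage efficacy design without a toxicity rule.

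**Other controls.** SAEs are notified without delay (11.2.5.1). The sponsor's vigilance unit evaluates risk and benefit continuously (11.2.6). SUSARs, new events and urgent measures go to the authorities on set timelines (11.2.2, 11.2.6). Doses are adapted per patient (6.6), and the trial can be ended for drug safety problems (13.7). The synopsis sends periodic safety reports to the independent committee; 11.2.6 names only ANSM and the CPP as recipients.

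**The concern.** The formal toxicity counts end where most of the exposure begins. An unexpected serious reaction has a clear reporting route. A high rate of expected events, such as febrile neutropenia or hepatic toxicity, has no equivalent: section 11.2.3 lets frequency make a reaction unexpected but gives no figure. The vigilance unit may well notice such a build-up, but the supplied text does not oblige anyone to count events at a stated number of phase II patients and act on the count.

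The protocol's own evidence on the drug pairings is mixed. In the first doublet study, drug-related events led to modification, interruption or discontinuation in 69% of patients, with no comparator, and SN-38 AUC rose 1.44-fold, yet tolerability was called acceptable. Of the placebo-controlled FOLFIRI trial the synopsis says: "The combination was very tolerable, with little increase in toxicity compared to the control chemotherapy regimen". No DLT rate for the triplet with regorafenib is given. What is at stake is how many patients would be included before a poorly tolerated dose is formally reviewed.

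**Working it through.** **1. New patients in phase II.** Section 10.1 gives 87 = 18 + 69, with 6 of the 69 carried over from phase I. New patients: 69 − 6 = 63. Cross-check against the phase I maximum of 24: 87 − 24 = 63. The definition of the recommended dose also allows 0/3; if only three were treated there, the figure would be 69 − 3 = 66. The synopsis states six.

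**2. What six patients show.** Exact (Clopper-Pearson) 95% upper limits: 1 DLT in 6 gives 64%; 0 in 6 gives 46%. The chance that a tested dose shows at most 1 DLT in 6 is (1−p)^6 + 6p(1−p)^5, where p is the true three-cycle rate. At p = 0.40: 0.0467 + 0.1866 = 0.233.

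**3. An example bound.** Reviews after 15, 30 and 45 new patients complete cycle 3. Pause at the smallest count for which the posterior probability that the rate exceeds 1/3 is above 0.80. The target of 1/3 is my assumption, taken from the 2-in-6 stop in Table 2. With a Beta(1/3, 2/3) prior, the posterior probability is:

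| Review | Count | At this count | One event fewer |
|---|---|---|---|
| 15 | 7 | 0.843 | 0.684 |
| 30 | 13 | 0.863 | 0.764 |
| 45 | 18 | 0.816 | 0.723 |

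Beta(1/2, 1/2) and Beta(1, 1) priors give the same bound, 7/13/18.

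**4. Operating characteristics.** The plan gives no DLT rate for this regimen, so the rates are assumptions shown as a range. *Pass* is P(at most 1 of 6). *Fire* is an exact binomial recursion over the three reviews. *Unpaused* is pass × (1 − fire), treating the phase I and phase II counts as independent given the rate. *Mean included* is the sum over reviews of P(fire at that review) × (n + 7.2), plus P(no fire) × 63.

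| True rate | Pass | Fire | Unpaused | Mean included of 63 |
|---|---|---|---|---|
| 20% | 0.66 | 0.02 | 0.64 | 62 |
| 25% | 0.53 | 0.07 | 0.49 | 60 |
| 33% | 0.36 | 0.32 | 0.24 | 53 |
| 40% | 0.23 | 0.65 | 0.08 | 42 |
| 50% | 0.11 | 0.95 | 0.005 | 29 |

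Without a bound, the *unpaused* column equals the *pass* column.

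The 7.2 is the number included while the last patient in a review set completes three 14-day cycles. It assumes even accrual of 63 patients over the planned 12 months: 63/12 = 5.25 per month, and 5.25 × 42/30.44 = 7.2. The first review would thus fall at about 22 included and the third at about 52.

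**The case against.** **The missing source.** Appendix 12 is named in the sentence that creates the committee, and the word *first* implies later time points. The documents cannot settle whether dates or a bound exist there. This stands, and it makes the point conditional.

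**The existing layers.** Reporting, vigilance, dose rules and termination powers are real, and the trial is open-label. The evidence on the dose is also wider than the DLT window, since for phase I "Patients will be treated until disease progression", with adverse events recorded to 30 days after the last dose. A reader might infer that phase II has no safety oversight, or that the committee will not meet again. The documents support neither. The controls act per event, per patient or at discretion; what is absent from the supplied text is an obligatory check on the cohort.

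**The measure.** Under section 2.2.1, any drug-related non-hematologic event of grade 3 or more counts unless excepted. Hypophosphatemia is not excepted, and grade 3–4 cases occurred in 12% and 14% of patients in two doublet studies whose tolerability the plan describes favourably. Missing more than 7 daily regorafenib doses for toxicity also counts. An acceptable regimen could therefore have a DLT-type rate above 25%, and unneeded pauses would then exceed 7%. This stands: the committee must decide which events count.

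**The work.** Attribution, missed doses and whether hand-foot reaction was controllable would need adjudication in phase II. Blood counts on days 1 and 8 make grade 4 neutropenia lasting more than 3 days hard to establish. This also stands.

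**The gain.** At a 25% rate, the chance of passing phase I and completing phase II unpaused moves only from 0.53 to 0.49. That is as intended, because 25% is below the target. The gain lies at 40% (0.23 to 0.08) and 50% (0.11 to 0.005).

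**Conclusion.** The gap holds for the supplied text: no dated committee review and no pausing count for 63 new patients treated at a dose cleared in about six. It is a worthwhile, inexpensive improvement to patient safety, conditional on appendix 12. Confidence is medium because that appendix is unseen.

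The numbers rest on assumed true rates, a chosen target of 1/3, and only the six patients at the recommended dose being modelled. They describe when a review would be prompted and do not count lasting harm. A reader might take the 32% firing rate at a true rate of 33% as a failure of the bound. It is not: 33% lies at the target, so not firing there is not a miss. Nor do the figures show that the combination is too toxic; the documents give no DLT rate for it.

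**What to change.** Check appendix 12 first. If it holds phase II dates and a bound, change nothing; if it holds dates only, add the bound. Otherwise:

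- In 11.2.7, schedule reviews by the existing three-member committee after 15, 30 and 45 newly included patients complete cycle 3.
- Pause inclusion for committee review, with no automatic stopping, when a pre-written bound on phase I DLT-type events is reached; 7/15, 13/30, 18/45 is one example.
- Have the committee confirm the target rate and which events count, for instance whether asymptomatic grade 3 laboratory events such as hypophosphatemia do.
- State in 11.2.6 that the committee receives the periodic safety reports, as the synopsis says.
- Leave any death-triggered review to the committee charter.

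The cost is a protocol amendment, two or three extra committee reviews, and extension of DLT adjudication to phase II patients. With the example bound, an unneeded pause occurs in about 2% of trials at a true rate of 20% and 7% at 25%, and more often if an acceptable regimen has a higher DLT-type rate. Inclusion continues between reviews.

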## 12. Quality assurance and control

### 12.1. Data collection

#### Database management

The Database will be hosted by the Institut du Cancer Montpellier (ICM) – Val d'Aurelle, Unité de Biométrie – CTD INCa, [name] under the responsibility of [name].

Database management will be provided by an electronic Case Report Form (eCRF) developed using the CSOnline module of Ennov Clinical® software.

In case of a technical problem on the eCRF, the investigator may refer to the specific operating procedure of the eCRF or contact directly:

ICM – Unité de Biométrie – CTD INCa

From Monday to Friday 9am-5pm

Email: [[contact]](mailto:[contact])

[contact] Tél. : [name]

#### Secure access password

Each user will receive in his/her personal mailbox an access code (login) and a personal password automatically generated from CSOnline to connect to the eCRF via the following website: <https://ecrfval.icm.unicancer.fr/CSOnline/>.

A password non-disclosure certificate is signed by the principal investigator engaging his/her responsibility regarding the confidentiality of the access codes for all users of the eCRF in his/her center.

#### Data collection

The study data will be recorded directly by the identified and declared persons of each center, via the eCRF, and will be controlled and validated according to specific procedures.

At the end of the study and once all the eCRF data are validated, the investigator will log in and sign all the pages in order to validate the data entered for each patient.

The sponsor will create and send an electronic copy (PDF file) to the investigator. This copy must be printed and signed by the investigator, to be archived at the investigator's site.

## 12.2 Trial monitoring

To ensure the authenticity and credibility of all data, in accordance with the "Décision portant sur les Bonnes Pratiques Cliniques, 24 November 2006", the sponsor establishes a system of quality assurance consisting in:

- The management and monitoring of the trial according to the sponsor's (ICM) procedures;
- The data quality control of the investigational centers by the monitor which involves:
  - verifying that the protocol, as well as the current ICH-GCP guidelines and the national regulatory requirements are accurately followed,
  - verifying the informed consent and the eligibility of each patient
  - verifying that the e-CRF data is consistent and in concordance with the source documents,
  - verifying the notification of each SAE,
  - verifying the drug traceability (dispatching, storage and accountability),
  - verifying (if applicable) that patients are not already participating in another research trial which may exclude their inclusion in the present protocol. The monitor will also verify that patients have not participated in another trial following with, if applicable, an exclusion period before they can participate in another protocol,
- The audit of the participating investigational centers when deemed necessary;

The monitors and CRAs in charge of the trial monitoring will be mandated by the sponsor. They must have access to all the patients' data as necessary for their duty, in accordance with the national regulatory requirements. The monitors and CRAs are bound by professional secrecy under the national regulatory requirements. Written reports must be issued to ensure monitoring visit traceability.

In order to ensure the optimal research quality control, the investigator commits to provide the monitor with direct access to all the patients' files.

